## **7. ELIGIBILITY CRITERIA**

### **7.1 Overall Description of Trial Participants**

Patients with MCI, Patients with VascD and Patients with AlzD, together with age-, gender- and BP matched healthy volunteer control subjects (HC) will be recruited to enable the complete data analysis of 11 MCI Patients, 11 VascD Patients, 11 ALzD Patients and 11 HCs.

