## **5. OBJECTIVES**

### **5.1 Primary Objective**

To compare the beat-to beat cerebral blood flow velocity (CBFv) between patients with Mild Cognitive Impairment (MCI), patients with Vascular Dementia (VascD), patients with Alzheimer's Dementia (AlzD) and age-, gender- and blood pressure (BP)-matched healthy control (HC) subjects during performance of the Addenbrooke's Cognitive III (ACE-III) examination

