to ensure they meet the study specific inclusion and exclusion criteria. Participants will only be referred to the researcher if the direct care team, based on the patient's cognitive functioning and clinical assessment determine that the patient will have capacity to consent to the study. Capacity will then be assessed formally by the researcher at the initial stage of information provision and at the formal consent process after a cooling off period of up to 7 days. These patients will be introduced to the researcher by the responsible clinical physician or specialist nurse for the provision of further study specific information, in the form of *Participant (Patient) Information Leaflet*. After provision of study specific information, the researcher will assess the patient's capacity in accordance with the Mental Capacity Act 2005. This is a 2 stage process where firstly, there must be a concern that the patient may lack capacity (in this case due to cognitive impairment). When the study information is provided to participants, it will be assessed in 4 steps. Firstly, the ability to understand the information, secondly to weigh up the information, thirdly to retain the information, and finally be able to communicate the decision back to the researcher. This initial discussion and assessment will take place at the outpatient memory clinic and stroke clinic at the LPT and UHL respectively, or through the participant's preferred contact method if recruiting from Join Dementia Research.

Age-, gender-, BP-matched HC will be recruited from University of Leicester departmental volunteers, patients' relatives and friends, and by poster advertisement (using *Research Participant Poster*) displayed in outpatient clinics at the University Hospital of Leicester (UHL) NHS Trust. Care will be taken to ensure that the HC are matched to the patients in terms of age, gender, and medical co-morbidities. HC will be provided with a volunteer specific information leaflet (*Participant (Volunteer) Information*).

After study specific information has been provided to the patients or volunteers, the researcher's contact details will be provided at the end of the PIS and the patient or volunteer will be able to contact the researcher directly if they wish to participate in the study.

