Participants who contact the researcher to be included in the study will be made an appointment to attend the Cerebral Haemodynamics in Ageing and Stroke Medicine (CHIASM) laboratory at the Leicester Royal Infirmary to undergo formal consent using the Participant (Patient or Volunteer) Consent Form. At this point, the researcher will then explain the nature and purpose of the research again and answer any questions that the

participant, may have. Capacity will be re-assessed at this time using the process described above and in accordance with the principles of the Mental Capacity Act 2005.

Formal consent will then be obtained as detailed in Section 8 and the participant will be enrolled into the study.

All participants will have their travel expenses reimbursed.

If a patient or volunteer expresses an interest in the study at the initial stage but does not make contact with the researcher within 7 days, a follow-up reminder letter (*Patient Follow-up Letter*) will be sent to the patient through the direct care team with the researcher's contact details.

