## 8. STUDY PROCEDURES

### 8.1 Informed Consent and Assessment of Capacity

Following provision of study specific information, the potential research participant (Volunteer or Patient) will be able to contact the researcher with the contact details provided to confirm willingness to participate in the study. At this time an appointment will be made to attend the Leicester Royal Infirmary to undergo formal consent and capacity assessment as outlined below.

Participant consent form must be in place before the undertaking of any research project-specific assessments, using the current version (*Participant (Volunteer or Patient) Consent Form*) which has been approved by the National Research Ethics Service and the local Trust Research and Development Department. Written and verbal versions of the current approved Participant (Volunteer or Patient Information Leaflet, Participant (Patient or Volunteer) Consent Form or will be presented detailing no less than: the exact nature of the study; the implication and constraints of the protocol; the known side effects and any risks involved in taking part. It will be clearly stated that the participant is free to withdraw from the study at any time for any reason without prejudice to future care, and with no obligation to give the reason for withdrawal.

At the time of consent, the researcher will re-assess the patient's capacity in accordance with the Mental Capacity Act 2005. This is a 2 stage process where firstly, there must be a concern that the patient may lack capacity (in this case due to cognitive impairment). When the study information is provided to participants, it will be assessed in 4 steps. Firstly, the ability to understand the information, secondly to weigh up the information, thirdly to retain the information, and finally be able to communicate the decision back to the researcher. This initial discussion and assessment will take place at the outpatient memory clinic and stroke clinic at the LPT and UHL respectively.

The person who obtains consent and performs the capacity assessment must be suitably qualified and experienced, and have been authorised to do so by the Chief/Principal Investigator (CI/PI), as detailed on the Delegation of Authority and Signature log for the study. The original signed Informed Consent form will be retained at the study site within the Investigator Site File (ISF). A copy of the signed Informed Consent form will be given to

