#### **8.4 TCD Assessment**

For all subjects, all assessments will be undertaken in a dedicated cardiovascular research laboratory at Leicester Royal Infirmary (LRI), which is at a controlled temperature (20-24°C) and is free from distraction. Participants will be asked to refrain from heavy meals, strenuous exercise, alcohol, smoking and caffeine for four hours prior to attending the research laboratory. The subject will sit on an examination couch. Baseline casual BP will be calculated as a mean of three supine brachial BP readings using a validated UA767 BP monitor. Beat-to-beat non-invasive BP will be recorded continuously using the Finometer cuff device (Finapres Medical Systems; Amsterdam, The Netherlands) attached to the middle finger of the non-dominant hand. R-R interval will be recorded using a 3-lead ECG. End-tidal partial pressure of carbon dioxide (EtCO2) will be monitored using small nasal cannulae placed at the base of the nose (Salter Labs, ref 4000) attached to a capnograph (Capnocheck Plus) to monitor the breathing. Simultaneous bilateral insonation of the middle cerebral arteries (MCAs) will be performed using TCD with 2MHz probe using a Viasys Companion III, with the subject either sitting or lying supine on a couch (in the case of difficult to insonate windows). The vessel will be located via the temporal bone window, and identified as the MCA by the waveform, its depth, velocity, and the direction of flow. All parameters will be simultaneously recorded onto a computer software system (PHYSIDAS), providing data for subsequent off-line analysis. A head frame will be used to secure the ultrasound probes in position and to minimise their movement. Once satisfactory signals have been obtained, four recordings will be made:

- 1) A 5 minute baseline recording during which the patient sits quietly with their eyes open
- 2) A recording during which the participant undertakes the Attention, Memory, and Fluency tasks of the ACE-III Cognitive Examination.
- 3) A recording during which the participant undertakes the language tasks of the ACE-III Cognitive Examination.
- 4) A recording during which the participant undertakes the visuospatial ability, and final memory tasks, of the ACE-III Cognitive Examination.

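### Controls are described as BP-matched in six sections, but no enrolment, eligibility, replacement or analysis rule in the protocol ensures it

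*Combined protocol and SAP*

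**What the plan says.** The primary objective (5.1) compares the patient groups with "age-, gender- and blood pressure (BP)-matched healthy control (HC) subjects during performance of the Addenbrooke's Cognitive III (ACE-III) examination". The label recurs in the synopsis (section 2), the rationale (section 4), the first secondary objective (5.2), 7.1 and 7.2. Section 7.1 says that the patient groups "together with age-, gender- and BP matched healthy volunteer control subjects (HC) will be recruited", and sets 11 controls against three patient groups of 11.

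On how matching is done, 7.2 has two adjacent sentences. The first, on where controls come from, calls them matched for age, gender and BP. The second states what will be attended to: "Care will be taken to ensure that the HC are matched to the patients in terms of age, gender, and medical co-morbidities". BP is not in that second list.

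On timing, 7.2 places enrolment at consent: "Formal consent will then be obtained as detailed in Section 8 and the participant will be enrolled into the study". Section 8.1 bars earlier study measurements: "Participant consent form must be in place before the undertaking of any research project-specific assessments". The window check (8.2) and demographic data (8.3, with no BP item) follow. The first BP reading described is in 8.4: "Baseline casual BP will be calculated as a mean of three supine brachial BP readings".

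Sections 7.3 and 7.4 contain no BP criterion, and no tolerance or matching ratio is given. Section 8.7 replaces a control only on withdrawal. Section 11.1 plans baseline comparisons with Bonferroni correction and a repeated measures ANOVA, and names neither a BP covariate nor a matched analysis.

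**The concern.** Matching on BP is part of the comparison named in the primary objective. If the protocol is followed as written, nothing makes the controls' BP resemble the patients', and a control whose BP is far from theirs stays in. A report that called the controls BP-matched would then claim a property that recruitment had not created.

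BP is not an incidental variable here. Section 4 treats it as the input signal and CBFv as the output in transfer function analysis, and describes ARI as an index of how far flow depends on pressure. It also names hypertension among the vascular risk factors associated with AlzD. Section 7.3 requires VascD patients to have focal signs consistent with stroke and imaging evidence of cerebrovascular disease. Controls come from departmental volunteers, relatives, friends and poster respondents (7.2). A systematic BP difference is therefore plausible, and a group difference in CBFv or ARI could partly reflect it.

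**Working it through.** **Does any step act on BP?** Following a control through the protocol:

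| Step | Section | Role of BP |
|---|---|---|
| First contact and information | 7.2 | none described |
| Matching care | 7.2 | not among the factors listed |
| Eligibility | 7.3, 7.4 | no criterion |
| Consent and enrolment | 7.2, 8.1 | none |
| Window check, demographics | 8.2, 8.3 | none |
| Doppler session | 8.4 | measured for the first time |
| Discontinuation, replacement | 8.7 | not a reason |
| Analysis | 11.1 | no BP term |

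BP is measured after enrolment, and no later rule depends on it.

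**How large could a chance gap be?** The group size of 11 is from 7.1 and 11.2 and is not contested here. The documents give no SD for systolic BP, so 15, 18 and 20 mmHg are assumptions. Suppose there is no true difference and no effective matching.

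SE of a difference in means = SD × √(2/11) = 0.426 × SD.

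P(|gap| > 10 mmHg) = 2 × [1 − Φ(10/SE)].

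| Assumed SD (mmHg) | SE (mmHg) | 10/SE | One patient-control contrast | At least one of three |
|---|---|---|---|---|
| 15 | 6.4 | 1.56 | 12% | 27% |
| 18 | 7.7 | 1.30 | 19% | 42% |
| 20 | 8.5 | 1.17 | 24% | 50% |

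The last column is from a simulation of 1,000,000 draws in which the three patient groups share one control group. With an SD as low as 12 mmHg, the two probabilities are 5% and 13%. Any systematic difference would come on top.

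**Would the planned baseline comparison reveal a real gap?** For a true difference of 10 mmHg, a two-sided t-test at 5% with 11 per group (20 degrees of freedom, noncentrality 10/SE) has power of 32% for SD 15 and 20% for SD 20. Section 11.1 does not say how many comparisons the Bonferroni correction covers. If it covers all six pairs of the four groups, power falls to 11% and 6%. A non-significant baseline test would therefore be weak evidence of matching.

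**The case against.** Four counter-arguments deserve an answer.

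- **Silence is not prohibition.** Nothing forbids asking a volunteer about a known BP before booking, and matching on co-morbidities may bring in diagnosed hypertension indirectly. This stands. A reader might infer that the design makes BP matching impossible, but the documents do not support that. They show only that no step ensures it.
- **Section 7.2 does mention BP.** The sentence just before the one on matching care calls the controls BP-matched. A reader might infer that 7.2 drops BP and so contradicts 7.1. It does not. The defect is narrower: two adjacent sentences name different factors, and the one describing what is done leaves BP out.
- **The effect on the outcomes is not shown.** Section 4 describes the transfer of BP fluctuations, not of resting level. The CBFv parameter in 6.2 is a percentage change, and the main test is a repeated measures ANOVA, so a stable resting difference bears less directly on that parameter than on absolute CBFv. This also stands. A reader might infer that the CBFv or ARI results will be biased by some amount, but the documents give nothing from which to compute it.
- **A gap need not be hidden.** Baseline BP is recorded (8.4), and baseline data are compared between groups (11.1). A report could show the values. That helps transparency, but the comparison triggers no action and has low power at this size.

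**Conclusion.** The concern holds as a mismatch between what the protocol claims and what it does: BP matching is stated six times, including in the primary objective, and no procedure brings it about. This is more than a missing detail, because following the protocol to the letter would leave a stated feature of the primary comparison without support. The study can still run, and the repair is cheap, so it should be made without being treated as fatal.

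The chance-gap figures of about 12% to 24% for one contrast rest on the assumed SDs, approximate normality, equal SDs across groups and no true difference. They describe imbalance in BP, not bias in CBFv or ARI. The procedural finding does not depend on them.

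**What to change.** **Preferred: make the label true.** Take the three brachial readings already planned in 8.4 right after consent. Moving them is not enough on its own, because 7.2 enrols the participant at consent. So amend 7.2 to say that a control is accepted into the matched group only after the reading, against a target fixed in advance. The target must suit one control group facing three patient groups, for example frequency matching to the patients' BP distribution. A band around any single patient would not balance the controls against each group. If the patient groups differ in BP, one control group cannot match all three, and the protocol should say which distribution is the target. Section 8.7 should give the status of controls who are not accepted, and 6.2 should say whether they count in the percentages of recruited subjects.

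Cost: no extra measurements, but some volunteers are turned away after attending, and enough patients must be measured first to define the target.

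**Otherwise: drop the claim.** Delete the BP-matched label in sections 2, 4, 5.1, 5.2, 7.1 and 7.2 together, since a partial deletion would create a new inconsistency. Handle BP in the 11.1 comparison with the baseline readings already collected, for example as a covariate. Cost: wording and one model term, with the caution that adjustment relies on the groups' BP ranges overlapping.

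**Either way,** make the two sentences in 7.2 name the same matching factors as 7.1.

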### **7.2 Recruitment Process**

Patient recruitment at the site will only commence once the research team has ensured that the following approval/essential documents are in place:

- Research Ethics Committee (REC) approval
- HRA approval
- Final Sponsorship approval
- NHS Trust Research and Development Department (R&D) approval
- Signed delegation of duties and responsibilities logs

Suitable MCI patients, AlzD patients and VascD patients will be identified at the specialist memory clinics at Leicester Partnership NHS Trust, and in the stroke and geriatric outpatient clinic at University Hospitals of Leicester NHS Trust, according to a study-specific list of inclusion and exclusion criteria (detailed in next section). We will also be using Join Dementia Research (JDR) as a recruitment tool. This is an online self-registration service that enables volunteers with memory problems or dementia, carers of those with memory problems or dementia and healthy volunteers to register their interest in taking part in research. The purpose of JDR is to allow such volunteers to be identified by researchers as potentially eligible for their studies. Researchers can then contact volunteers, in line with the volunteers' preferred method of contact, to further discuss potential inclusion. Eligibility screening will be conducted by the specialist nurses or consultants who are part of the direct clinical care team. They will only refer potential participants who meet the eligibility criteria and who have capacity to consent to the researcher. The researcher will not access patients' medical records until formal written consent has been obtained. Participants recruited from Join Dementia Research will be screened by the researcher through discussion with the participant and their carers, friends or relatives, or GP surgery

to ensure they meet the study specific inclusion and exclusion criteria. Participants will only be referred to the researcher if the direct care team, based on the patient's cognitive functioning and clinical assessment determine that the patient will have capacity to consent to the study. Capacity will then be assessed formally by the researcher at the initial stage of information provision and at the formal consent process after a cooling off period of up to 7 days. These patients will be introduced to the researcher by the responsible clinical physician or specialist nurse for the provision of further study specific information, in the form of *Participant (Patient) Information Leaflet*. After provision of study specific information, the researcher will assess the patient's capacity in accordance with the Mental Capacity Act 2005. This is a 2 stage process where firstly, there must be a concern that the patient may lack capacity (in this case due to cognitive impairment). When the study information is provided to participants, it will be assessed in 4 steps. Firstly, the ability to understand the information, secondly to weigh up the information, thirdly to retain the information, and finally be able to communicate the decision back to the researcher. This initial discussion and assessment will take place at the outpatient memory clinic and stroke clinic at the LPT and UHL respectively, or through the participant's preferred contact method if recruiting from Join Dementia Research.

Age-, gender-, BP-matched HC will be recruited from University of Leicester departmental volunteers, patients' relatives and friends, and by poster advertisement (using *Research Participant Poster*) displayed in outpatient clinics at the University Hospital of Leicester (UHL) NHS Trust. Care will be taken to ensure that the HC are matched to the patients in terms of age, gender, and medical co-morbidities. HC will be provided with a volunteer specific information leaflet (*Participant (Volunteer) Information*).

After study specific information has been provided to the patients or volunteers, the researcher's contact details will be provided at the end of the PIS and the patient or volunteer will be able to contact the researcher directly if they wish to participate in the study.

Participants who contact the researcher to be included in the study will be made an appointment to attend the Cerebral Haemodynamics in Ageing and Stroke Medicine (CHIASM) laboratory at the Leicester Royal Infirmary to undergo formal consent using the Participant (Patient or Volunteer) Consent Form. At this point, the researcher will then explain the nature and purpose of the research again and answer any questions that the

participant, may have. Capacity will be re-assessed at this time using the process described above and in accordance with the principles of the Mental Capacity Act 2005.

Formal consent will then be obtained as detailed in Section 8 and the participant will be enrolled into the study.

All participants will have their travel expenses reimbursed.

If a patient or volunteer expresses an interest in the study at the initial stage but does not make contact with the researcher within 7 days, a follow-up reminder letter (*Patient Follow-up Letter*) will be sent to the patient through the direct care team with the researcher's contact details.

### **7.3 Inclusion Criteria**

- Informed volunteer consent, patient consent
- Male or female, aged between 18 and 100 years of age
- Able (in the Investigator's opinion) and willing to comply with all study requirements
- Willing to allow his or her General Practitioner (GP) to be notified of participation in the study
- Good understanding of written and verbal English

#### **Healthy Controls-specific Inclusion Criteria**

- No evidence of subjective or objective memory impairment on cognitive testing
- No major medical co-morbidity (outlined in detail in the exclusion criteria) or medication use that could adversely affect cognition

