#### **MCI Patient-specific Inclusion Criteria**

Clinical diagnosis of MCI made by a specialist\* in a patient who fulfils the established clinical consensus criteria for MCI [NIA/AA 2011] specifically:

- Concern regarding a change in cognition compared to the person's previous level, by the patient and/or informant

- Objective evidence of impairment of one or more cognitive domains, greater than expected for age, and educational background, over time if repeated measures are available.
- Preserved independence of functional abilities and minimal to no impairment on complex instrumental functions
- Not demented

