#### **Alzheimer's Dementia Specific Inclusion Criteria**

Clinical Diagnosis of AlzD made by a specialist\* in a patient who fulfils the NIA/AA criteria for Probable AlzD, specifically:

- Meets the criteria for dementia
  - The memory impairment and cognitive deficits cause significant impairment in social or occupational functioning, and represent a significant decline from a previous level of functioning, not explained by a delirium or a major psychiatric disorder
  - Impairment of at least two cognitive domains
- Insidious or gradual onset
- Clear history of worsening cognition by report or observation

- The initial and most prominent cognitive deficits are evident on history and examination in one of the following domains:
  - Amnestic: impaired learning and recall of recently learned information
  - Non amnestic: language/visuospatial/executive dysfunction
- No evidence of substantial cerebrovascular disease, core features of dementia with lewy bodies, features of frontotemporal dementia, prominent features of semantic variant primary progressive aphasia, evidence of active neurological disease, a non-neurological co-morbidity or medication that could affect cognition

*\*A specialist being defined as a psychiatrist or a geriatrician, or a specialist mental health nurse with a specific interest or expertise in cognitive disorders.*

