### **9.3 Incidental Findings**

Any unexpected or incidental findings in Volunteers or Patients, such as, high blood pressure, abnormal heart rhythm, undiagnosed cognitive impairment (volunteers), cerebral blood flow velocity suggestive of intracranial pathology or carotid artery stenosis will be reported to the patient or volunteer's GP for further investigation. This will only be with the patient or volunteer's permission and written consent (*Participant (Patient or Volunteer) Consent Form*), and is expressly stated in the *Participant (Patient or Volunteer) Information Sheet*.

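### The only cognitive criterion for healthy controls covers memory, so an undiagnosed volunteer with a purely non-memory deficit can enter as a control

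*Combined protocol and SAP*

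**What the plan says.** Section 7.3 gives healthy controls two specific criteria. The first is "No evidence of subjective or objective memory impairment on cognitive testing". The second is "No major medical co-morbidity (outlined in detail in the exclusion criteria) or medication use that could adversely affect cognition", which concerns possible causes of a deficit and not the deficit itself.

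For MCI, 7.3 asks for "Objective evidence of impairment of one or more cognitive domains, greater than expected for age, and educational background". Memory need not be the domain affected. The same list also asks for "Concern regarding a change in cognition compared to the person's previous level, by the patient and/or informant", largely preserved function and absence of dementia, all under a "Clinical diagnosis of MCI made by a specialist". For Alzheimer's dementia, one accepted presentation is "Non amnestic: language/visuospatial/executive dysfunction".

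Section 9.3 foresees that cognitive impairment may come to light in a volunteer. Its only consequence is a report to the GP, with the volunteer's permission.

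**The concern.** The patient definitions span all cognitive domains and the control definition spans one. Applied as written, and even with a complete test result in hand, the control rule passes a volunteer who is impaired in attention, fluency, language or visuospatial ability, provided memory is intact and not complained of.

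This matters because the study compares CBFv and ARI between groups while participants perform ACE-III tasks, and those tasks draw on these other domains as well as on memory. If such a control responds partly like a patient, the control mean moves towards the patient mean and the spread among controls grows. Both effects make a true difference harder to detect. With 11 controls, each person is one eleventh of the group, and the same controls serve every patient-versus-control comparison.

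**Working it through.** **Step 1: does any other rule close the gap?**

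| Place | Content relevant to a control with a non-memory deficit |
|---|---|
| 7.2 Recruitment | Controls come from departmental volunteers, patients' relatives and friends, and clinic posters. They are matched on age, gender, BP and co-morbidity. No cognitive rule. |
| 7.3 General inclusion | Consent, age, compliance, GP notification, English. No cognitive rule. |
| 7.3 Control-specific | Memory only, plus co-morbidity and medication. |
| 7.4 Exclusion | Age, compliance, pregnancy, co-morbidity affecting autoregulation. No cognitive rule. |
| 8.7 Withdrawal | Inability to comply, consent withdrawn, loss of capacity. Controls are replaced only on withdrawal. |
| 9.3 Incidental findings | Report to the GP. No exclusion or replacement. |

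Nothing removes such a volunteer.

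**Step 2: scope of the rule.** The ACE-III maxima in Appendix B are attention 18, memory 26, fluency 14, language 26 and visuospatial 16, total 100. Domains outside the control rule hold 100 − 26 = 74 points. This describes scoring, not recording time: in 8.4, memory tasks appear in two of the three task recordings, and only the language recording has none.

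**Step 3: the plan's own sample-size statement.** Section 11.2 states 11 per group, 2 ARI units, 80% power, 5% significance. No SD is given, so the 11 cannot be reproduced directly. Back-solving a two-sided two-sample t-test gives SD = 1.592, a standardised contrast of d = 2 / 1.592 = 1.256. This figure comes from an ARI statement; the documents give nothing comparable for CBFv.

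**Step 4: illustration of dilution (assumptions, not findings).** Let k of 11 controls be shifted by a fraction f of the contrast towards the patient mean, with unit SD otherwise.

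- Expected contrast: d × (1 − f × k/11).
- Added variance within the control group: (f × d)² × k × (11 − k) / (11 × 10).

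Example with k = 1, f = 1: the contrast is 1.256 × 10/11 = 1.142 SD (1.82 ARI units). The added variance is 1.577 × 10/110 = 0.143, so the pooled SD is √(1 + 0.143/2) = 1.035.

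Simulated t-test power, two-sided 5%, 11 versus 11:

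| Impaired controls | f = 1 (fully like patients) | f = 0.5 | f = 0.25 |
|---|---|---|---|
| 0 | 80% | 80% | 80% |
| 1 | 70% | 76% | 78% |
| 2 | 58% | 71% | 76% |
| 3 | 47% | 66% | 74% |

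Counting only the smaller mean difference at f = 1, and not the added spread, gives 72%, 63% and 53%.

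**Step 5: how likely is at least one such control?** The documents give no rate for volunteers with a non-memory deficit alone. For an assumed rate p the chance is 1 − (1 − p)¹¹:

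| Assumed p | 2% | 5% | 10% | 20% |
|---|---|---|---|---|
| At least one among 11 | 20% | 43% | 69% | 91% |

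Section 4 says MCI affects up to 20% of older adults, but that covers all MCI, so the rate of interest should be lower.

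**The case against.** The strongest reply is that the effect may be small. Section 4 reports, from limited data, that CBFv has not been found to differ significantly between MCI and controls unless the comparison is restricted to amnesic MCI. On that account the subtype that differs is the one the memory criterion already bars. This stands as a caution on size. It does not settle the matter, because Section 4 treats the task-evoked studies separately, and the remark says nothing about ARI.

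A second reply is that memory is used loosely. The criterion speaks of cognitive testing, and 7.2 uses memory problems as an umbrella term. That may be the intent, but 9.3 uses the wider term when it describes impairment in volunteers, and an eligibility rule is applied as written. If the wider meaning was intended, the edit simply records it.

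A reader might also infer that the control and MCI groups overlap outright, so that anyone failing a non-memory domain is an MCI case. The documents do not support this: 7.3 also requires concern about change, preserved function, no dementia and a specialist diagnosis. Formal overlap is limited to a person with non-memory MCI and no memory complaint or deficit. The practical risk is the undiagnosed volunteer in a similar state.

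**Conclusion.** The gap in the control criterion is real, and no other section closes it. It can admit controls with a non-memory deficit, and any effect would tend towards no difference, most directly in the comparison with MCI.

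Its size cannot be derived from the documents. The power figures rest on a contrast of 1.256 SD back-solved from the ARI statement, on a pairwise t-test without Bonferroni correction in place of the planned repeated measures ANOVA, and on assumed values of k and f. The 70%, 58% and 47% column is the worst case of those shown.

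A reader might conclude that power will fall that far, or that all three contrasts shrink equally. Neither follows. Nothing shows that these volunteers respond like patients, and for the two dementia contrasts a full shift would treat a functioning volunteer as a dementia patient. Nor do the 74 non-memory points show that non-memory tasks make up most of the recordings. What remains is a well-defined weakness in eligibility wording, of unknown effect, that is cheap to remove.

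**What to change.** In the control-specific criteria of 7.3, replace *memory impairment* with *impairment in any cognitive domain (attention, memory, fluency, language or visuospatial)*, applied to both subjective complaint and objective testing. The control rule then mirrors the MCI definition. The five domains listed are those of the ACE-III, which every participant already undertakes, so no new instrument is needed.

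The criterion at present names no test or cut-off. Naming them at the same time would keep the wider rule from being applied unevenly, and one sentence should state how a control found impaired on the ACE-III is handled in the analysis.

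The cost is a few words in 7.3. The downside is that a few more volunteers may be screened out, including some wrongly labelled as impaired if five domains are checked without a stated threshold.
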